6.1 Information to be collected at screening

HLA-Cw6 determination will be performed at screening for patients who have provided written informed consent. A central laboratory will be used to determine Cw6. Patients will thereafter be stratified into the two cohorts. TNF α -308 polymorphism will be centrally determined at the same time.

6.2 Patient demographics/other baseline characteristics

The following data will be gathered/documentated at visit 2 (day -14 to -7):

- Demographic data [age, sex, race, ethnicity, and childbearing potential (for females only)].
- Verification of inclusion/exclusion criteria.
- History (medical, smoking, psoriasis).
- Previous psoriasis therapies in the 6 months prior to study entry.
- A chest X-ray, an ECG and HCV, HBV (HBsAg, HBsAb, HBcAb), HIV tests will be required unless performed within the previous 6 months. Adequate documentation (assessment reports, tracking and imagines as applicable) must be available for previous evaluations to be considered valid at baseline.

- A Quantiferon TB-Gold test or PPD test will be required unless performed within the previous 3 months. Adequate documentation (assessment report) must be available for previous evaluations to be considered valid at baseline.
- Height, weight and waist.
- Physical examination (only as source document).
- Vital signs (heart rate, blood pressure).
- PASI, IGA mod 2011.
- Hematology, blood chemistry, urinalysis.
- Serum pregnancy test.
- ██████████

Treatment with secukinumab will begin at visit 3 (day 1), during which the following data will be collected/documented:

- Verification of inclusion/exclusion criteria.
- Physical examination.
- Vital signs.
- Height (if not obtained at visit 2), weight and waist.
- Hematology, blood chemistry.
- High sensitivity C-reactive protein (hsCRP).
- PASI, IGA mod 2011.
- DLQI, HADS.

6.3 Treatment exposure and compliance

Data on investigational drug will be reported on the Dosage Administration Record (DAR) of the eCRF in order to provide information about drug exposure.

6.4 Efficacy

6.4.1 Psoriasis Area and Severity Index (PASI)

The primary efficacy variable is the measurement of the severity of psoriasis using the Psoriasis Area and Severity Index (PASI) ([Richard GB et al. 2013](#)), the most widely used tool for this purpose. PASI combines the assessment of the severity of lesions and the area affected into a single score with a range of 0 (no disease) to 72 (maximal disease). The PASI will be assessed at each visit from V2 to V12 of the core study and at all four visits of the extension period.

A PASI score ([Weisman et al. 2003](#)) will be calculated as indicated in [Appendix 3](#). The head, trunk, upper limbs and lower limbs are assessed separately for erythema, thickening (plaque elevation, induration), and scaling (desquamation). The average degree of severity of each sign in each of the four body regions is assigned a score of 0-4. The area covered by lesions

on each body region is estimated as a percentage of the total area of that particular body region. In particular:

1. The neck is assessed as part of the head.
2. The axillae and groin are assessed as part of the trunk.
3. The buttocks are assessed as part of the lower limbs.
4. When scoring the severity of erythema, scales should not be removed.

Because the head and neck, upper limbs, trunk and lower limbs correspond to approximately 10%, 20%, 30% and 40% of the body surface area, respectively, the PASI score is calculated using the formula:

$$\text{PASI} = 0.1(\text{EH}+\text{IH}+\text{DH})\text{AH} + 0.2(\text{EU}+\text{IU}+\text{DU})\text{AU} + 0.3(\text{ET}+\text{IT}+\text{DT})\text{AT} + 0.4(\text{EL}+\text{IL}+\text{DL})\text{AL}$$

Usually, a PASI 75 improvement is used as a minimum threshold to evaluate the clinical efficacy of new psoriasis treatments (Callen JP et al. 2003). A PASI 90 improvement will be used as primary endpoint in this study.

The following definitions of PASI will be used in this study:

- PASI 50 response: subjects achieving $\geq 50\%$ improvement (reduction) in PASI score compared to baseline are defined as PASI 50 responders.
- PASI 75 response: subjects achieving $\geq 75\%$ improvement (reduction) in PASI score compared to baseline are defined as PASI 75 responders.
- PASI 90 response: subjects achieving $\geq 90\%$ improvement (reduction) in PASI score compared to baseline are defined as PASI 90 responders.
- PASI 100 response / remission: complete clearing of psoriasis (PASI=0).

6.4.2 Investigator's Global Assessment Scale (IGA)

The IGA mod 2011 rating scale for overall psoriatic disease is shown in [Appendix 4](#). The IGA mod 2011 scale has been developed based on a previous version of the scale used in secukinumab Phase II studies in collaboration with health authorities, in particular the FDA. The explanations/descriptions of the points on the scale have been improved to ensure their differentiation. The IGA mod 2011 will be evaluated at each visit from V2 to V12 of the core study and at all four visits of the extension period. It measures the severity of the disease on a five-point scale ranging from 0 (no disease, 'clear') to 4 ('very severe') (Richard GB et al 2013).

Based on this scale, a subject will be considered as IGA 0 or 1 responder if the subject achieves a score of 0 or 1 and improved by at least 2 points on the IGA scale compared to baseline.

6.4.3 Appropriateness of efficacy assessments

The PASI is widely considered the gold standard for assessing psoriasis severity in a clinical trial setting (Richard GB et al. 2013). The PASI score, the assessment of the severity of the psoriasis symptoms and the extent to which the subject's body area is affected by the disease,

is considered acceptable by health authorities ([CHMP/EWP/2454/02 2004](#)) to assess efficacy in conjunction with Investigator's Global Assessment mod 2011 (IGA mod 2011).

6.5 Safety

6.5.1 Physical examination

An overall physical examination will be performed by the investigational staff at visit 2 and include the examination of general appearance, skin, neck (including thyroid), eyes, ears, nose, throat, lungs, heart, abdomen, back, lymph nodes, extremities, vascular and neurological. A short physical exam will include the examination of general appearance and vital signs (blood pressure and pulse) and will be performed at all visits starting from visit 3.

Detailed information on each evaluated apparatus from all physical examinations must be included in the source documentation at the study site.

Metabolic syndrome will require any 3 of the following 5 criteria: increased waist circumference (≥ 102 cm for men, ≥ 88 cm for women), elevated triglycerides (≥ 150 mg/dl), reduced high-density lipoprotein (HDL) cholesterol (≤ 40 mg/dl in men and ≤ 50 mg/dl in women), elevated blood pressure (≥ 130 mmHg systolic and ≥ 85 mmHg diastolic or ongoing treatment for hypertension) or elevated glucose (≥ 100 mg/dl or ongoing treatment for elevated glucose) ([Expert Panel JAMA 2001](#)).

6.5.2 Vital signs

Sitting blood pressure and heart rate will be measured at visits 2 and 3 and then at each visit starting from visit 7. Clinically notable vital signs are defined in [Appendix 1](#).

6.5.3 Height, weight and waist

Height in centimeters (cm) will be measured at visit 2 or 3 only.

Body weight (to the nearest 0.1 kilogram in indoor clothing, but without shoes) and waist will be measured at visits 2, 3 and 12 of the core study and at all four visits of the extension period. BMI will be derived from weight and height results.

6.5.4 Laboratory evaluations

6.5.4.1 Hematology

Hemoglobin, hematocrit, red blood cell count, white blood cell count with differential (e.g. neutrophils, basophils, eosinophils, monocytes, lymphocytes), and platelet count will be measured at visits 2 and 3 and then at each visit starting from visit 7 (including extension period). [Appendix 1](#) shows the extended laboratory ranges that are considered clinically notable.

6.5.4.2 Clinical chemistry

Albumin, alkaline phosphatase, total bilirubin, bicarbonate/CO₂, calcium, cholesterol, chloride, creatinine, creatine kinase (CK), gamma-glutamyl transpeptidase (GGT), glucose, lactate dehydrogenase (LDH), inorganic phosphorus, lipase, amylase, magnesium, potassium,

total protein, AST, ALT, sodium, triglycerides, urea/blood urea nitrogen (BUN) and uric acid will be measured at visits 2 and 3 and then at each visit of the core study starting from visit 7.

The following clinical chemistry assessments will be run at all four visits of the extension period: albumin, alkaline phosphatase, total bilirubin, calcium, cholesterol, creatinine, CK, GGT, glucose, LDH, potassium, total protein, AST, ALT, sodium, triglycerides, uric acid.

[Appendix 1](#) shows the extended laboratory ranges that are considered clinically notable.

6.5.4.3 Urinalysis

Dipstick measurements for specific gravity, protein, glucose and blood will be performed. WBC and RBC sediments will also be analyzed at visits 2, 10 and 12 of the core study and at all four visits of the extension period.

6.5.4.4 hsCRP

hsCRP will be assessed at visits 3, 10, and 12 of the core study and at all four visits of the extension period.

6.5.5 Electrocardiogram (ECG), chest X-ray

An ECG and chest X-ray will be required at visit 2 unless performed within the previous 6 months. Adequate documentation (assessment reports, tracking and images as applicable) must be available for previous evaluations to be considered as baseline.

6.5.6 Pregnancy and assessments of fertility

A serum pregnancy test will be performed at visit 2 in all fertile women.

6.5.7 Appropriateness of safety measurements

The safety assessments selected are standard for this indication/patient population.

6.6 Other assessments

6.6.1 Resource utilization

The amount of resources used during the study will be evaluated in comparison with the 6 months prior to the beginning of the study.

Resource utilization will be extrapolated from data collected from single items in the flow chart such as “medical history, psoriasis medical history, concomitant medications and adverse events.”

6.6.2 Health-related Quality of Life

Quality of life will be assessed by means of the Dermatology Life Quality Index (DLQI), a validated, 10-item general dermatology disability index designed to assess health-related quality of life in adult subjects with skin diseases such as eczema, psoriasis, acne, and viral warts (Finlay AY et al. 1994). The measure is self-administered and includes domains of daily activities, leisure, personal relationships, symptoms and feelings, treatment, and work/school activities. The DLQI has well-established reliability and validity as determined in several studies (Shikiar et al 2003, Badia X et al. 1999, Lewis V et al. 2004, Shikiar et al. 2006).

Moreover, it is frequently used in clinical psoriasis trials, has been tested across 32 different skin conditions and is available in 55 languages. The recall period is the previous week, and the instrument requires 1 to 2 minutes to complete. Each item has four response categories ranging from 0 (not at all) to 3 (very much). “Not relevant” is also a valid response and is scored as 0. The DLQI[©] total score is a sum of the 10 questions. Scores range from 0 to 30 and higher scores indicate greater health-related quality of life impairment. Each subscale of the DLQI[©] may be analyzed separately.

Patients will be asked to complete the questionnaire at visits 3, 10 and 12 of the core study and at visits 2 and 4 of the extension period.

Completed questionnaires will be reviewed and examined by the investigator before the clinical examination for responses that may indicate potential AEs or SAEs. The investigator should review not only the responses to the questions in the questionnaires but also any unsolicited comments written by the patient.

If the occurrence of AEs or SAEs is confirmed, the physician must record the events as per instructions given in [Section 7.2](#) of the protocol.

[figure not shown]

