2.2 Secondary objectives

- To compare the proportion of responders to PASI 50/75/90/100 between cohorts at each time point.
- To compare the mean changes vs baseline in the Investigator's Global assessment (IGA) mod 2011 between cohorts at each time point.
- To compare time to reach PASI 90 between cohorts.
- To compare time to reach PASI 75 between cohorts.
- To evaluate the quality of life by means of the Dermatology Life Quality Index (DLQI) in all patients at each time point.
- To evaluate anxiety and depression using the Hospital Anxiety and Depression Scale (HADS) in all patients at each time point.
- To evaluate the correlation between HADS and PASI in all patients.
- To evaluate changes from baseline in weight, BMI and waist in all patients at each time point.
- To compare safety and tolerability between cohorts during the 24 weeks, and thereafter for up to 72 weeks.
- To evaluate the amount of resources used during the study in comparison with the 6 months prior to the beginning of the study.

3 Investigational plan

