4.1 Inclusion criteria

Patients eligible for inclusion in this study have to fulfill **all** of the following criteria:

1. Subject must be able to understand and communicate with the investigator and comply with the requirements of the study and must give written, signed and dated informed consent before any study related activity is performed.
2. Men or women at least 18 years of age at time of screening.
3. Diagnosis of moderate to severe chronic plaque-type psoriasis for at least 6 months (including concomitant psoriatic arthritis as per the Classification Criteria for Psoriatic Arthritis criteria [CASPAR]).
4. Moderate to severe psoriasis as defined at enrollment by:
 - PASI score ≥ 10
 - or
 - PASI score > 5 but < 10 and DLQI ≥ 10
5. Patients that are candidates for systemic therapy, whether treatment naïve or after failed response to other systemic therapy (i.e. cyclosporine, methotrexate and PUVA) or to an anti-TNF α (or is intolerant and/or has a contraindication to these).

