6.6.3 Hospital Anxiety and Depression Scale (HADS)

The Hospital Anxiety and Depression Scale (HADS) is a fourteen-item scale that generates ordinal data. Seven of the items relate to anxiety and seven relate to depression. This outcome measure was specifically developed to avoid reliance on aspects of these conditions that are also common somatic symptoms of illness, for example fatigue and insomnia or hypersomnia. Calculations of scores: each of the 14 items is rated on a 4-point scale (‘Yes, definitely’, ‘Yes, sometimes’, ‘No, not much’ and ‘No, not at all’). All items except 7 and 10 are scored as ‘Yes, definitely’ = 3 to ‘No, not at all’ = 0. Items 7 and 10 are scored as ‘Yes, definitely’ = 0 to ‘No, not at all’ = 3. The HADS consists of two sub-scores: the HAD-A for anxiety and HAD-D for depression; each sub-score ranges from 0 to 21 points; scores ≥ 11 indicate the presence of anxious or depressive disorders; scores between 8-10 points are borderline abnormal, and scores of ≤ 7 indicate that the disorder is not present.

Patients will be asked to complete the questionnaire at visits 3, 10 and 12 of the core study and at visits 2 and 4 of the extension period.

Completed questionnaires will be reviewed and examined by the investigator before the clinical examination for responses that may indicate potential AEs or SAEs. The investigator should review not only the responses to the questions in the questionnaires but also any unsolicited comments written by the patient.

If the occurrence of AEs or SAEs is confirmed, the physician must record the events as per instructions given in [Section 7.2](#) of the protocol.

7 Safety monitoring

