81%	0,89	53%	47%	193	172	365	215	192
81%	0,92	52%	48%	190	175	365	212	195
81%	0,96	51%	49%	186	179	365	207	199
81%	1,00	50%	50%	182	182	364	203	203

The choice of clinically relevant differences is based on the following considerations:

- As the efficacy of secukinumab has already been clinically substantiated through extensive Phase II and III programs, all patients will be treated with active drug using the same therapeutic regimen (no placebo comparison will be done).
- The primary variable is the proportion of patients who reach PASI 90 after 16 weeks. This endpoint is quite challenging and much more restrictive compared to PASI 75. Only the investigator is responsible for collecting the components or scoring signs and total regional areas in the PASI assessment. Therefore, it has great internal variability, which should be taken into account.
- The paper on HLA-Cw6 ustekinumab data ([Talamonti M et al. 20134](#)) revealed a striking difference between Cw6-positive and Cw6-negative patients in the proportion of PASI 90 achievements, 85.7% vs 56.5%. This difference in PASI 90 is very relevant in the daily clinical management of patients.

Considering the above statements, it seems reasonable to claim that more than halving the difference observed with ustekinumab between Cw6-positive and Cw6-negative patients, secukinumab would be an advantage in terms of efficacy for Cw6-negative patients who do not respond properly to ustekinumab and other approved biologic drugs.

Although the sample size was calculated considering only Cw6 haplotype, it is also adequate for regression models assessing differences from baseline for clinically relevant variables. In fact, the expected number of patients who reach PASI 90 at week sixteen is at least 250 (roughly 71% of 365). Therefore, using a conservative criterion of a minimum of 10 “events” for each predictor in the model, we can add up to 25 variables in the model without loss of power ([Vittinghoff E et al. 2007](#)). This model will take into account variables such as BMI, smoking, metabolic syndrome and TNF α -308 polymorphism, which, among the six existing polymorphisms, is the one most greatly affecting response to treatment with anti-TNF α drugs.

10 Ethical considerations

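### The investigator, who alone scores PASI, is told to read the completed DLQI and HADS before the clinical examination, so every same-visit HADS-PASI pair may come from a rater who has just read the HADS (minor; cheap to improve).

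*Protocol*

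**What the plan says.** **Order of review.** Protocol Section 6.6.2 (DLQI) states: "Completed questionnaires will be reviewed and examined by the investigator before the clinical examination for responses that may indicate potential AEs or SAEs". Section 6.6.3 (HADS) repeats the sentence. The review is a full reading: "The investigator should review not only the responses to the questions in the questionnaires but also any unsolicited comments written by the patient".

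**Who scores PASI.** Protocol Section 9.7: "Only the investigator is responsible for collecting the components or scoring signs and total regional areas in the PASI assessment". It then says of the PASI assessment: "Therefore, it has great internal variability, which should be taken into account".

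**When.** Section 6.6.3 schedules the HADS at core visits 3, 10 and 12 and at extension visits 2 and 4. Section 6.6.2 gives the DLQI the same schedule. For PASI, Section 6.4.1 says: "The PASI will be assessed at each visit from V2 to V12 of the core study and at all four visits of the extension period".

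**What the pairs are used for.** Section 2.2 lists as a secondary objective: "To evaluate the correlation between HADS and PASI in all patients". Protocol Section 9.5.4 and SAP Section 2.11 plan a Spearman or Pearson coefficient, described as explored, and a cross-table of PASI 75/90 response against HADS sub-scores of 11 or more.

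**Blinding.** Section 3.1 blinds patients and investigators to Cw6 status. Section 5.4 says the study is open label. No separate PASI assessor is named.

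**The concern.** A correlation between a patient-reported score and a clinician-rated score is informative only if the two are obtained independently. Here one person reads how anxious or depressed the patient feels and may then grade erythema, thickening, scaling and area, a rating the protocol itself calls variable. If knowing the answers shifts the grading even slightly towards them, part of any HADS-PASI association comes from the rating procedure and not from the disease.

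At stake is the interpretation of one secondary objective. HADS is collected only at visits under this order, so the trial has no unaffected same-visit pairs to use in a sensitivity analysis.

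**Working it through.** The point is procedural. The check sets the visit schedule, the rater and the order of review side by side. The plan gives no figure for this effect, so there is none to reproduce.

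**1. Do the visits coincide?** (Protocol Tables 6-1 and 6-2, Sections 6.4.1 and 6.6.3)

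| Visit | Week | HADS/DLQI | PASI |
|---|---|---|---|
| V3 | 0 | yes | yes |
| V10 | 16 | yes | yes |
| V12 | 24 | yes | yes |
| E2 | 48 | yes | yes |
| E4 | 72 | yes | yes |
| V2, V4–V9, V11, E1, E3 | other | no | yes |

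PASI is scored at 11 core visits (V2 to V12) and 4 extension visits, 15 in all. HADS is collected at 5 of them. All 5 possible same-visit pairs fall under the review-first instruction.

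**2. Is the rater the reader?** Yes. Sections 6.6.2 and 6.6.3 assign the review to the investigator, and Section 9.7 assigns PASI scoring to the investigator alone.

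**3. Does the review precede PASI scoring?** This step is an inference. The instruction places the review before the clinical examination, which is not defined. PASI is an investigator's inspection of the skin at the same visit, so the plain reading includes it. The visit 3 list in Section 6.2 and the rows of Table 6-1 name PASI and IGA ahead of DLQI and HADS, but both are inventories of assessments and set no sequence. No other text puts PASI or IGA first.

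**4. How large could the effect be?** The documents give no value for how far a rater's score moves with the answers. The following is an assumption, shown as a range. Suppose there is no true association and, in standardised units, recorded PASI = noise + b × HADS. Then the induced Pearson correlation is

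r = b / √(1 + b²).

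With n = 365 (the evaluable number in Section 9.7), the smallest correlation significant at the two-sided 5% level is about tanh(1.96/√(365 − 3)) = tanh(0.103) = 0.103.

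| Assumed b | r from formula | Mean simulated Spearman | Share of trials with p < 0.05 |
|---|---|---|---|
| 0.05 | 0.050 | 0.05 | about 16% |
| 0.10 | 0.100 | 0.10 | about 45% |
| 0.15 | 0.148 | 0.14 | about 77% |
| 0.20 | 0.196 | 0.19 | about 94% |

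The induced correlation is almost equal to b, so the table returns its own assumption. It shows only that at this sample size a small shift would be enough to give a nominally significant but weak correlation. It is not evidence that any shift occurs. SAP Section 2.11 bases the quality-of-life analyses on the Safety set, so the actual n would differ from 365.

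**The case against.** **The order is inferred.** The instruction serves adverse event detection. The protocol places the physical examination under safety (Section 6.5.1), where from visit 3 the short examination covers general appearance and vital signs. PASI sits under efficacy (Section 6.4.1) and has its own row in Table 6-1. A site could properly score PASI before opening the questionnaires. This stands: the documents leave the order open and do not require PASI to come second. It is also a reason to write the order down.

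**The analysis is exploratory.** The correlation carries no hypothesis or alpha level. This stands, and it limits the severity.

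**Reordering does not blind the rater.** By week 16 the investigator has already read the visit 3 answers and has asked about adverse events at each visit. This stands. The remedy removes only the same-visit influence.

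**A reader might infer that baseline PASI is pushed up to the entry threshold, inflating PASI 90.** Criterion 4 in Section 4.1 accepts "PASI score > 5 but < 10 and DLQI ≥ 10", so an investigator who has read a DLQI below 10 knows that PASI must reach 10. The documents do not support the inference. The incentive exists only in patients with a low DLQI, where a pull towards the answers would lower PASI, so the two supposed effects oppose each other. Scoring PASI before seeing the DLQI could extend the incentive to every borderline patient. PASI is also scored at visit 2, when no DLQI has yet been collected. The number of patients affected cannot be derived.

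**A reader might also infer that the primary non-inferiority comparison is compromised.** Investigators are blinded to Cw6, so knowing the answers gives them no direct way to favour a cohort. Rating error that is equal in both cohorts can pull a difference towards zero, but the documents give no error rate and nothing that ties one to the questionnaire review.

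**Conclusion.** The point holds as a minor one. As written, the plan allows every same-visit HADS-PASI pair to be produced by a rater who has just read the HADS, and nothing in the protocol or SAP prevents it. This could bias the HADS-PASI correlation and the related cross-table. The size is unknown and cannot be derived from the documents.

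The conclusion rests on two things. The first is the plain reading that the clinical examination includes skin assessment, which the protocol does not state. The second is the general premise that a subjective score can be influenced by information the rater has just read.

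The point does not extend to the primary Cw6 contrast, the sample size, the entry threshold or the PASI 90 response rates.

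**What to change.** In Protocol Sections 6.6.2 and 6.6.3, replace the sentence on review order with a stated sequence:

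1. The patient completes the questionnaires.
2. The investigator scores and records PASI and IGA mod 2011 without having seen them.
3. The investigator reviews the questionnaires, including any comments, for potential AEs or SAEs at the same visit, before the rest of the clinical examination.

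Add a line to site training. For visits already carried out under the present text, the report should say that the order was not fixed and give this as a limitation of the HADS-PASI analysis.

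**Cost.** One sentence changes in two sections. No staff, visit or procedure is added. The safety review takes place a few minutes later in the visit. The rater still knows answers from earlier visits, so the bias is reduced but not removed.
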